For the safety outcomes, patients who were recruited but did not receive the intervention drug will be compared to patients who did receive the intervention drug to determine if their rates of adverse effects are similar. However, the sample size in this study is too low to perform formal non-inferiority tests on this data.

5. Study Intervention/Investigational Agent

Study intervention:

Patients will be randomized to six groups: 2 mg/kg (the lowest dose approved by the FDA), 1 mg/kg, 0.5 mg/kg, 0.25 mg/kg, 0.125 mg/kg of sugammadex and placebo (normal saline).

The Grady Memorial Hospital operating room pharmacy will store and dispense the study drug, while the anesthesia provider in the operating room will administer it.

As elaborated before, sugammadex is a FDA-approved drug that is in routine clinical use for NMB reversal.

Page 7 of 30 Version: 3 (10/14/2024)

² Heart rate < 60 beats per minute over two or more recordings if not present pre-operatively

³ Heart rate > 100 beats per minute over two or more recordings if not present pre-operatively

⁴ Systolic blood pressure < 90 mmHg and/or mean arterial pressure < 65 mmHg over two or more recordings

The study protocol was submitted to the U.S. FDA, and found to be exempt from IND regulations (PIND 162798 dated 2022-Jul-13).

6. Procedures Involved

This project is a double-blind randomized placebo-controlled dose-response trial that aims to determine the time taken to achieve adequate reversal comparing five doses of sugammadex as rescue therapy following inadequate reversal with neostigmine.

We will identify patients in the Grady Memorial Hospital OR who are scheduled to undergo an elective surgery under general anesthesia, received rocuronium for NMB and neostigmine for NMB reversal, and achieved a TOF count of at least 3 twitches but not a TOF ratio of 0.9 fifteen minutes after neostigmine has been given.

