These patients will be randomized using the Emory University REDCap (Research Electronic Data Capture) software to six groups: 2 mg/kg (the lowest dose approved by the FDA), 1 mg/kg, 0.5 mg/kg, 0.25 mg/kg, 0.125 mg/kg of sugammadex and placebo. Doses would be based on actual body weight. The time taken to reach a TOF ratio of 0.9 thereafter would be measured. If the patient fails to achieve this goal by 10 minutes, sugammadex would be given in 2 mg/kg increments until the patient reaches this threshold and can be safely extubated. The TOF ratio would be measured again at 30 minutes after arrival at the PACU to exclude delayed residual NMB with the plan to give further 2 mg/kg doses of sugammadex if detected.

The inclusion of a placebo group would allow us to examine if patients may recover spontaneously over that time without needing any sugammadex at all, and what parameters may predict that subset of patients. It will also improve the dose response modelling, in that randomization has been weighted so that patients who are least likely to need sugammadex (i.e. if they achieved a TOF count of 4 twitches without fade) are more likely to be in the placebo group or at the lowest dose of sugammadex that is being tested.

The time taken to a TOF ratio of 0.9 after the intervention drug has been given would be compared for statistically significant differences, controlling for the:

- TOF count (3 twitches, 4 twitches with fade, 4 twitches without fade), and
- TOF ratio (0 to < 0.9)

15 minutes after neostigmine has been given and prior to giving the intervention drug.

Quantitative neuromuscular monitoring will be carried out using electromyography, which measures the TOF ratio every 20 seconds. The TOF count (between 0 to 4) and the TOF ratio (0 to 1) would be measured and recorded at baseline and after administration of the study drug. If the TOF ratio remains < 0.9 after this, or if the patient exhibits any symptoms or signs of residual NMB blockade, a further 2 mg/kg dose of sugammadex would be given until the patient achieves a TOF ratio of 0.9.

Page 8 of 30 Version: 3 (10/14/2024)

7. Statistical Analysis Plan

Power Analysis

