An *a priori* power analysis was conducted using G*Power 3.1.9.4 (20). We used an ANOVA F-Test for one-way omnibus difference between groups, alpha threshold of 0.05 for rejecting the null hypothesis, statistical power of 0.80 and a "very large" effect size of 0.765 was calculated based on results from a 2013 randomized controlled trial that examined time from TOF count = 4 to TOF ratio 1.0 comparing neostigmine to three different doses of sugammadex: 0.5, 1.0, and 2.0 mg/kg (15). This gave a required sample size of N=24. This number was increased to N=36 to account for patients with poor modeling from a high starting TOFR (resulting in few data points for that patient) or incomplete recovery within the maximum ten minutes allotted. An anticipated 70% of those enrolled will become ineligible because of an initial TOFR of 90% or greater, thus not requiring any medications, so up to 120 patients may need to be recruited and screened, but only 36 will receive any treatment.

Methodology

Randomization will occur with permuted block randomization, divided into 18 groups, to ensure proportional allocation of participants in each group over time. Dose randomization will be assigned after stratifying by initial TOFC, with a set number of patients recruited for each group, as seen the table below. This ensures that patients who likely need a lower dose are more likely to receive it. Randomization will not occur until participation is assured, i.e., their TOFR is <0.90.

Table 1: Randomization plan for patients (n=36)

| Sugammadex Dose (mg/kg) → | | 0.00 | 0.125 | 0.25 | 0.50 | 1.00 | 2.00 | | | |
|---------------------------|-----------------|------|--|----------|------------|---------|---------|------|-------|----|
| Initial TOFR | Initial TOFC | Fade | placebo | | | | | | Total | |
| ≥ 0.9 | NA | NA | No treatment; track for adverse events | | | 0 | | | | |
| | | 4 | No | 3 pt | 3 pt | 2 pt | 2 pt | 1 pt | 1 pt | 12 |
| < 0.9 | 4 | Yes | 2 pt | 2 pt | 2 pt | 2 pt | 2 pt | 2 pt | 12 | |
| | 3 | NA | 1 pt | 1 pt | 2 pt | 2 pt | 3 pt | 3 pt | 12 | |
| < 0.9 | 0-2 | NA | No t | treatmen | t; track f | or adve | se even | ts | 0 | |
| Total # of Patients (pt) | | | 6 | 6 | 6 | 6 | 6 | 6 | 36 | |

Statistical Methodology

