Assuming assumptions are valid, an increasing exponential regression model with random intercept will be fitted with Time of Four Ratio versus Time, stratified by the natural log of the five dose levels (modeled below). This translates to a slow response initially followed by a more rapid response later. The random intercept will allow for different initial TOFR values.

Page 9 of 30 Version: 3 (10/14/2024)

$$TOFR = \frac{1}{B}e^{(A+time)/B} + TOFR_{initial} + C * \ln(dose)$$

"Success" will be defined as TOFR of ≥0.9 within 5 minutes for 95% of patients, following the model estimate, adjusting for the 95% confidence intervals of the estimates, based on initial TOF ratios, which may be grouped as needed. A secondary analysis will be conducted by TOFC to determine optimal dose at each TOFC level, and if TOFC correlates strongly with TOFR.

8. Data and/or Specimen Banking

N/A

9. Sharing of Results with Participants

N/A

10. Study Timelines

All subjects are anticipated to participate in the study from the start of their surgery to the time of their discharge from the PACU, which should be on the same day. It is expected that 1 year would be required to enroll all study subjects, and for the study to be completed by July 2023.

11. Inclusion and Exclusion Criteria

Individuals will be screened for eligibility at the anesthesia pre-admission clinic.

Inclusion criteria:

- Patients aged 18 years and above who will
- Undergo an elective surgery in the main operating room or outpatient surgery center at Grady Memorial Hospital,
- Receive general anesthesia (standardized to sevoflurane for maintenance),
- Receive rocuronium for NMB,
- Receive neostigmine for NMB reversal,
- Achieve a TOF count of at least 3 twitches but not a TOF ratio of 0.9 fifteen minutes after neostigmine has been given, and
- Able and willing to provide informed consent.

Exclusion criteria:

Page 10 of 30 Version: 3 (10/14/2024)

- Pregnancy and/or lactating,
- BMI ≥ 40,
- Severe renal impairment, i.e. chronic kidney disease stages IV and V as defined by GFR < 30 ml/min/1.73 m² (21),
- Severe hepatic impairment, i.e. Child-Pugh score C⁵ (22, 23),
- Pre-existing neuromuscular disease,
- Anticipated need for postoperative intubation, and/or
- Known hypersensitivity reactions to rocuronium, neostigmine and/or sugammadex.

12. Population

We will not be including the following special populations:

- Adults unable to consent
- Individuals under the age of 18 years
- Pregnant women

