- Did not require general anesthesia for surgery,
- Did not require NMB,
- Did not receive neostigmine for NMB reversal,
- Had a TOF count < 3 or a TOF ratio ≥ 0.9 fifteen minutes after neostigmine, or
- Remained intubated in the immediate postoperative period.

As the study intervention is a one-time dose of the study drug in the OR, no further action should be required if the patient decides to later withdraw from the study. The study will be terminated when the number of participants has reached the required threshold.

17. Risk to Participants

The most common risks of sugammadex as listed by the FDA (5) include:

- Nausea (23-26%)
- Vomiting (11-15%)
- Pain (36-52%)

Uncommon but serious risks of sugammadex include:

- Hypotension (4-13%)
- Tachycardia (2-5%)

Page 12 of 30 Version: 3 (10/14/2024)

- Bradycardia (1-5%)
- Anaphylaxis (0.3%)

Notably, all of these are known to be risks of general anesthesia as well as surgery and are routinely monitored for and treated in the PACU.

18. Potential Benefits to Participants

All study subjects will have any residual NMB reversed, which will prevent any postoperative complications such as respiratory compromise or weakness.

19. Compensation to Participants

N/A

20. Data Management and Confidentiality

Data to be collected include:

- Baseline demographics: MRN, date of birth, sex (male/female), race (white, black, American Indian or Alaska Native, Asian, Native Hawaiian or Other Pacific Islander, two or more races), ethnicity (Hispanic or Latino, not Hispanic or Latino), weight (kg)
- ii. Preoperative details: ASA status (I-IV)
- iii. Surgery details: date of surgery, diagnosis, surgery, start case time (hr: min), end case time (hr: min)
- iv. Anesthesia details: if succinylcholine was used (Y/N), total amount of rocuronium given (mg), the last dose of rocuronium that was given (mg), the time that the last dose of rocuronium was given (hr:min), neostigmine dose (mg), the time that neostigmine was given (hr: min), the time that the study drug was given (hr: min).
- v. TOF ratio (0-1)
 - Before any paralytic is given at the start of the case
 - Before neostigmine is given at the end of the case
 - Before the study drug is given
 - 30 minutes after PACU arrival
- vi. TOF count (0-4 ± fade)
 - Before neostigmine is given at the end of the case
 - Before the study drug is given
- vii. The time taken to achieve a TOF ratio of 0.9 (seconds).

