Data on serious adverse events such as death, perioperative cardiac arrest, and unplanned hospitalization as well as any other adverse events will also be collected up to the time of PACU discharge for both study participants as well as screen failures (participants who were recruited but not enrolled in the trial due to not fulfilling the study inclusion criteria).

Monitoring Table 3

| DSMP Requirement | How this Requirement is Met | Frequency | Responsible Party(ies) |
|---|--|---|---|
| Real-time review of participant data during | PI will review the data as it is being collected. | Every data collection | PI |
| initial data collection. | being conected. | timepoint | |
| | | Expectation is that this happens every | |
| | | time you obtain information. | |
| Site Monitoring at predetermined intervals: | There should be a standard operating procedure to review | Every 6 months | PI (self-assessment tool) |
| The Principal Investigator has a responsibility to ensure that the study is | data (whether a sample or 100%) at pre-determined intervals to ensure that there is | At a minimum, a review is required annually when no | Delegate a responsible party for each |
| following all aspects of the protocol. | adequate documentation of critical elements such as | one has been enrolled or the | requirement below. Self-assessment is |
| | eligibility criteria. Monitoring is required at the following | study is in long term follow up. | acceptable*. Self-assessment: a |
| | timepoints (but may be done more frequently): • study initiation • at least every six months | Additional risk- based interim monitoring may be required at least | process for self- assessment of protocol compliance and data integrity |
| | while participants are receiving intervention and | once every 12-24 weeks based on the site activity, to | which can be part of an overall DSMP. See CTAC's self- |
| | annually while participants are in follow-up | include the possibility of remote monitoring. | assessment tool on their webpage. |

Version: 3 (10/14/2024)

Page 16 of 30 IRB Form BIO 01192022

| | | A longer frequency | |
|---------------------------|--------------------------------------|-----------------------|--------------------|
| | | could be | |
| | | acceptable with | |
| | | justification about | |
| | | risk to participants. | |
| 100% review of | DCTR will review all regulatory | At study initiation | DCTR |

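### The safety control group is defined by not receiving study drug, so non-randomised patients given sugammadex clinically would count as unexposed

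*Combined protocol and SAP*

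**What the plan says.** Section 4 sets out the only planned between-group safety comparison: "patients who were recruited but did not receive the intervention drug will be compared to patients who did receive the intervention drug". It adds that the sample is too small for formal non-inferiority testing. Section 20 repeats that patients who do not qualify for study drug serve as the control group for the safety outcomes.

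To be randomised, a patient must, under Section 11, "Achieve a TOF count of at least 3 twitches but not a TOF ratio of 0.9 fifteen minutes after neostigmine has been given". Section 16 lists reasons for withdrawal, including not receiving neostigmine and "Had a TOF count < 3 or a TOF ratio ≥ 0.9 fifteen minutes after neostigmine". In Section 7, the Table 1 row for a TOF ratio below 0.9 with a TOF count of 0-2 has a total of 0 and, across the dose columns, the entry "No t | treatmen | t; track f | or adve | se even | ts" (one cell, broken by text extraction). The row for patients already recovered to 0.9 has the same entry.

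Section 18 states, with no limit to randomised patients: "All study subjects will have any residual NMB reversed, which will prevent any postoperative complications such as respiratory compromise or weakness". Section 21 describes non-qualifying patients as "screen failures (participants who were recruited but not enrolled in the trial due to not fulfilling the study inclusion criteria", whereas Sections 7 and 20 refer to them as enrolled.

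**The concern.** Not receiving study drug and not receiving sugammadex are different things, and the control group is built on the first. Section 5 describes sugammadex as in routine clinical use for reversal, and Section 3 describes both the ceiling effect of neostigmine and labelled uses of sugammadex that include deep block. It is therefore plausible that some non-randomised patients receive sugammadex from the clinical team: those with a TOF count of 0-2 after neostigmine, and those who never received neostigmine. The plan would place them on the unexposed side. If sugammadex changes the rate of nausea, vomiting, bradycardia, tachycardia or hypotension, mixing exposed patients into the controls pulls the compared rates together, in a comparison meant to show whether the rates are similar.

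A wording problem adds to this. A reader cannot tell whether the Section 18 statement reaches patients with a TOF count of 0-2, because their status differs between sections and Table 1 gives them the same label as recovered patients.

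**Working it through.** **1. Can the misclassification happen, and would the data show it?**
- Control definition (Sections 4 and 20): based on not receiving the intervention drug. Clinical sugammadex is not mentioned.
- Data list (Section 20, anesthesia details): rocuronium, neostigmine dose and time, and study-drug time. There is no field for non-study sugammadex. For non-qualifying patients, Section 20 names only baseline demographics and postoperative complications.
- Management text (Section 6): the 30-minute PACU check and the 10-minute rule, "If the patient fails to achieve this goal by 10 minutes, sugammadex would be given in 2 mg/kg increments until the patient reaches this threshold", are written for randomised patients after study drug. No section describes management of a TOF count of 0-2 at 15 minutes.

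So exposure among controls is possible and would not be visible in the planned dataset.

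**2. What the table label means.** Table 1 is a randomisation plan. Section 7 says only 36 patients will receive any treatment, and those 36 include the 6 on placebo. Treatment there means study allocation, so the natural reading of the row is that no study drug is given.

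**3. Whether Section 18 covers these patients.** For: Section 10 has subjects participating from the start of surgery, before the 15-minute count is known; Section 24 applies the term study subjects to people being consented; and Sections 7 and 20 call non-qualifiers enrolled. Against: they fail the Section 11 criterion, may be withdrawn under Section 16, and are screen failures in Section 21. The text does not settle it.

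**4. The plan's recruitment figure.** Inputs from Section 7: 36 treated, and 70% ineligible because the TOF ratio is already 0.9 or more.
- 36 / (1 − 0.70) = 120, as stated.
- 120 × 0.70 = 84, and 84 + 36 = 120. This leaves no patient for the TOF count 0-2 row.

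**5. Share of controls.** The documents give no rate *s* for a TOF count of 0-2, so 2%, 5% and 10% are assumptions. With 84 recovered controls, share = 120*s* / (84 + 120*s*).

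| Assumed *s* | Patients in 120 | Share of controls |
|---|---|---|
| 2% | 2.4 | 2.4/86.4 = 2.8% |
| 5% | 6 | 6/90 = 6.7% |
| 10% | 12 | 12/96 = 12.5% |

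Other Section 16 withdrawals are not in these counts; the documents give no rate for them either.

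**6. Effect on the comparison.** Suppose all the TOF count 0-2 patients receive sugammadex and then have the treated group's event rate. The difference shrinks by share × true difference. For an assumed true difference of 10 points, that is 0.3, 0.7 or 1.3 points. For scale, with 36 treated, 84 controls and the 25% nausea rate from Section 21, the standard error of the difference is sqrt(0.25 × 0.75 × (1/36 + 1/84)) = 8.6 points.

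**The case against.** A reader might infer that Table 1 and Section 18 impose opposite rules, and that Table 1 followed literally leaves the most deeply blocked patients unreversed. The documents do not support that. The table allocates study drug, its use of treatment includes placebo, and these patients fail inclusion. Section 24 says participation has no bearing on clinical care, and no passage forbids routine reversal. Silence about routine care for people withdrawn before randomisation is ordinary scoping.

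It can also be said that the bias argument is conditional. It needs such patients to occur, to be given sugammadex specifically (which no passage states for them), and to have event rates that sugammadex changes. Even then the shift is small beside the standard error, and Section 4 already disclaims formal testing.

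All of this stands, and it limits the size of the point. It does not answer the definition itself: the control group ignores actual exposure, and the planned data could not show whether that mattered. Nor does it settle whom Section 18 covers.

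**Conclusion.** The point holds as a problem of exposure classification together with unclear wording. The control definition in Sections 4 and 20 can count sugammadex-exposed patients as unexposed, and no listed field would reveal it. The documents do not establish that reversal is withheld from anyone or that two rules directly oppose each other; that conflict would need the Table 1 label to mean more than no study drug, as well as Section 18 to cover screen failures.

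The expected effect is small: about 2.8%, 6.7% or 12.5% of controls for assumed TOF count 0-2 rates of 2%, 5% or 10%, with 84 recovered controls and every such patient exposed. Section 16 withdrawals for other reasons could add to this by an amount the documents do not allow one to estimate. The comparison is descriptive, and neither the primary outcome nor the sample of 36 depends on it. The change is still worth making because it is cheap and removes an avoidable bias from the only planned between-group safety comparison.

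**What to change.** - Relabel the Table 1 row for a TOF count of 0-2 as no study drug, not randomised.
- Reconcile Table 1 with Sections 16, 18 and 21: state whether Section 18 covers screen failures, and use enrolled in one sense throughout. Clinical management of these patients is for the investigator to specify; none is proposed here.
- Add one yes/no field in Section 20 for non-study sugammadex, taken from the anesthesia record, for every recruited patient who is not randomised.
- In Sections 4 and 20, restrict the safety control group to patients who received no sugammadex.
- Report patients with a TOF count of 0-2, and any other non-randomised patients exposed to sugammadex, separately.

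The cost is a wording amendment, one extra chart field and a slightly smaller control group. No change in sample size is needed for this point.

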A Cochrane systematic review published in 2017 (12) analyzed 41 randomized controlled trials of 4,206 adults who received non-depolarizing NMBAs for elective surgery, and found that a 2 mg/kg dose of sugammadex was 6.6 times faster (10.22 minutes) than a 0.05 mg/kg dose of neostigmine in reversing moderate NMB from the second twitch (T2) to a TOF ratio > 0.9, while

_

¹ The ratio of the fourth (T4) to the first (T1) twitch after a TOF stimulation

a 4 mg/kg dose of sugammadex was 16.8 times faster (45.78 minutes) than a 0.07 mg/kg dose of neostigmine in reversing deep NMB from a PTC 1-5 to TOF ratio > 0.9.

However, less is known when there is shallow NMB, i.e. when the TOF count is 4 but there is still detectable TOF fade. Concerningly, Kirkegaard *et al.* found in 2002 that the maximal 0.07 mg/kg dose of neostigmine was unable to reverse all patients to a TOF ratio of 0.9 within 30 minutes, even at a pre-intervention TOF count of 4 (13). Whether a lower dose of sugammadex would be sufficient to achieve a TOF ratio of 0.9 after shallow NMB has been examined by Schaller *et al.* in 2010 and Pongrácz *et al.* in 2013. The former group found that in a group of 94 adults undergoing elective surgery, a dose of 0.22 mg/kg of sugammadex was equivalent to a dose of 0.034 mg/kg of neostigmine in reversing NMB from a TOF ratio of 0.5 to 0.9 within 5 minutes in 95% of their patients (14). Conversely, Pongrácz's group found that a 0.5 mg/kg dose of sugammadex reversed NMB from a TOF count of 4 to a TOF ratio of 1.0 in 4.1 minutes on average compared to 2.1 minutes for a 1.0 mg/kg dose of sugammadex, 1.8 minutes for a 2.0 mg/kg of sugammadex, and 8.5 minutes for a 0.05 mg/kg dose of neostigmine (15).

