Due to the high cost of sugammadex, some researchers have hypothesized that a lower dose is required when combined with neostigmine. A 2015 study from Beirut in adults undergoing elective surgery demonstrated that a dose of 2 mg/kg of sugammadex combined with neostigmine 0.05 mg/kg was non-inferior to the standard dose of 4 mg/kg of sugammadex in reversing deep NMB, defined as returning from a TOF count of 0 to a TOF ratio of 0.9 within 5 minutes, with similar times to extubation as well as no cases of recurarization in the post anesthetic care unit (PACU) (16). Lobaz, Sammut and Damodaran reported in 2013 the use of sugammadex as rescue therapy for a 71-year-old patient with end stage renal disease who was unable to be weaned off the ventilator almost five hours after receiving a single 1.2 mg/kg dose of rocuronium. He had initially achieved a TOF of 4, was reversed with 2.5 mg of neostigmine 45 minutes after induction, but failed to maintain adequate spontaneous ventilation despite his TOF remaining at 4, and was transferred to the intensive care unit 3 hours post induction. There, his TOF steadily declined to 2, as a result of which he received a 6 mg/kg dose of sugammadex, causing him to be successfully extubated ten minutes later (17). It is similarly important to dose sugammadex appropriately; Carollo et al. published a case report in 2019 of an 8-month-old patient who had recurarization after a 4 mg/kg dose of sugammadex was given with a TOF count of 2/4, which fortunately resolved after a second 4 mg/kg dose of sugammadex (18).

Lastly, known common adverse effects of neostigmine include bradycardia, nausea and vomiting (19), while the use of sugammadex has been found to lead to nausea, vomiting, hypotension and headache in \geq 10% of patients (5). There have also been case reports of marked bradycardia possibly leading to cardiac arrest with the use of both agents.

Page 6 of 30 Version: 3 (10/14/2024)

4. Study Endpoints

Primary study outcome:

The time taken to achieve a TOF ratio of 0.9 after the use of the intervention drug versus placebo in a patient population that has already received neostigmine for NMB reversal.

Secondary study outcome:

The percentage of patients who achieve a TOF ratio of 0.9 within 1 minute, 2 minutes, 5 minutes, and 10 minutes.

Safety outcomes:

The incidence in PACU (measured in %) of:

- i. Nausea,
- ii. Vomiting,
- iii. Bradycardia²,
- iv. Tachycardia³, and
- v. Hypotension⁴.

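### The SAP's only model has no value for placebo, and dose shifts the level of the TOF ratio, not the speed of recovery, so the times behind the 5-minute success rule are misspecified

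*Combined protocol and SAP*

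**What the plan says.** Section 7 (Statistical Methodology) gives the model as

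TOFR = (1/B)·e^((A+time)/B) + TOFR_initial + C·ln(dose),

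fitted with a random intercept and "stratified by the natural log of the five dose levels (modeled below". On the shape of the curve it says: "This translates to a slow response initially followed by a more rapid response later". On the intercept it says: "The random intercept will allow for different initial TOFR values". Success is a TOFR of at least 0.9 "within 5 minutes for 95% of patients, following the model estimate".

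Table 1 in Section 7 lists six groups of 6 patients, with placebo at dose 0.00. Section 4 defines the primary outcome as "The time taken to achieve a TOF ratio of 0.9 after the use of the intervention drug versus placebo". Section 6 says that times to 0.9 will be compared, controlling for TOF count (TOFC) and TOFR before study drug, but names no method. The one-way ANOVA appears only in the power calculation.

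**The concern.** The model has to turn dose into a time to reach 0.9, and the printed form is poorly suited to that. ln(dose) cannot be evaluated for placebo. Dose also enters only as an added constant. It lifts or lowers the whole curve, including the part at time 0 before the drug can have acted, and leaves the rate of recovery alone.

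The stake is the trial's main conclusion. The primary objective is to find an appropriate dose, and Section 7 reads success from this model. If the times for the active doses come from a level shift on one shared curve, a dose that meets the 5-minute rule may be called a failure, or the reverse. Placebo gets no model estimate to set against them.

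**Working it through.** **Inputs.** The equation, the shape statement and the success rule (Section 7); the group doses and sizes (Table 1); the mean recovery times quoted in Section 3 for 0.5, 1.0 and 2.0 mg/kg, namely "4.1 minutes on average compared to 2.1 minutes for a 1.0 mg/kg dose of sugammadex, 1.8 minutes for a 2.0 mg/kg of sugammadex". Those times run from a TOF count of 4 to a TOFR of 1.0 with no prior neostigmine described, so they are used for shape only. The SAP gives no figure for this model to reproduce.

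**1. Placebo.** ln(dose) is −2.08, −1.39, −0.69, 0 and 0.69 for 0.125 to 2 mg/kg, and undefined at 0. The model can use 30 of 36 patients. An improvised ln(dose + c) is no neutral repair: it places placebo at −6.91 with c = 0.001 and at −2.08 with c = 0.125.

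**2. Speed.** The derivative over time is (1/B²)·e^((A+time)/B). It contains no dose.

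**3. Time 0.** The model gives TOFR_initial + (1/B)e^(A/B) + C·ln(dose).
- The gap is C·ln 2 = 0.69C per doubling and C·ln 16 = 2.77C from 0.125 to 2 mg/kg. For assumed C of 0.05, 0.1 and 0.2 that is 0.14, 0.28 and 0.55 TOFR units.
- If TOFR_initial is the measured baseline, the curve cannot match it at two doses unless C = 0.
- If it is an estimated random intercept, it and C·ln(dose) are both constants within a patient. C is then a difference in average level between dose groups. It also picks up the baseline imbalance that Table 1 builds in: TOFC 3 makes up 1 of 6 patients on placebo and on 0.125 mg/kg, but 3 of 6 on 1 and on 2 mg/kg.

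**4. Implied times.** Write E(t) = (1/B)e^((A+t)/B). For a common start and a fixed target, E(t_d) = constant − C·ln(d), so

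E(t_0.5) − E(t_1) = E(t_1) − E(t_2) = C·ln 2.

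A slow start followed by faster recovery requires B > 0. E is then convex, and t_0.5 − t_1 < t_1 − t_2: each doubling must save more time than the last. The quoted means show 4.1 − 2.1 = 2.0 min, then 2.1 − 1.8 = 0.3 min.
- Match 4.1 and 2.1: t_2 < 2.1 − 2.0 = 0.1 min (quoted 1.8).
- Match 2.1 and 1.8: t_0.5 < 2.1 + 0.3 = 2.4 min (quoted 4.1).
- Match 4.1 and 1.8: at time 0 the 2 mg/kg curve has already covered at least 1 − 1.8/4.1 = 56% of the distance from the 0.5 mg/kg start to the target.

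A grid of B from 0.5 to 10,000 min agrees. In the first case t_2 is at most 0.0996 min, negative for B of 3 to 20, with no solution for B of 2 or less. The time-0 share runs from 0.99 down to 0.561.

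**5. Negative B.** The equal-step condition becomes 2 = e^(−2.0/b) + e^(0.3/b) with b = −B. Its root is b = 0.436, where the terms are 0.010 and 1.990. So B of about −0.44 min fits all three times, but it describes fast-then-slow recovery, against the SAP's statement. The curve then levels off at TOFR_initial + C·ln(dose). At 1 mg/kg, ln(dose) = 0, so if TOFR_initial is the measured baseline (below 0.9 by eligibility), that group could never reach 0.9.

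**6. Illustration of the consequence (assumed curves).** Recovery curves that saturate at 1 were generated with dose acting on the rate. Times to 0.9 from a start of 0.4 were set by a log-log line through the three quoted means, extrapolated to 0.125 mg/kg. Readings came every 20 s and stopped at 0.9; starts were 0.2, 0.4, 0.6 and 0.8. The SAP equation was fitted by least squares with B > 0.
- Start 0.2, doses 0.5, 1 and 2 mg/kg: true times 4.37, 2.89 and 1.92 min; fitted 7.19, 6.44 and 5.60. Three successes are read as failures.
- Start 0.6, dose 0.125 mg/kg: true 6.63 min, fitted 4.19. A failure is read as a success.
- Start 0.8: negative fitted times for four of five doses.

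**The case against.** The strongest reply is that the equation is being read too literally.

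- **Placebo.** Naming five dose levels suggests that placebo was left out on purpose. The comparison with placebo would then rest on Section 6, and the secondary outcome gives observed percentages at 0.9 by 1, 2, 5 and 10 minutes without a model. Choosing among active doses does not need a placebo estimate. This is fair as far as it goes. But no rule states the exclusion, Section 6 says that including placebo will improve the dose-response modelling, and the Section 6 comparison has no named method.
- **Stratified.** If this means a separate curve for each dose, A and B may differ and speed can vary with dose. Steps 2 to 5 would then not apply. But the equation does not index A or B by dose, and C·ln(dose) could not be separated from the intercept. In the illustration, per-dose curves came closer to the true times but still gave negative times at every dose from a start of 0.8.
- **Sign of B.** The equation does not fix it, and a negative B reproduces the quoted times. That requires dropping the SAP's stated shape and meets the plateau problem in step 5.
- **Benchmark.** Three means from another setting, without standard deviations and with nothing below 0.5 mg/kg, cannot size the bias. This stands, and so does the dependence of step 6 on assumed curves.
- **Baseline.** The SAP groups success by initial TOFR and adds an analysis by TOFC, and Section 6 controls for both. This reduces the imbalance problem but does not put dose on the rate.

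**Conclusion.** The concern holds as a must-fix point, with high confidence in the structural fault. As printed, the model has no value for 6 of 36 patients (17%), gives all doses the same recovery speed, and places a dose gap of 2.77C at time 0. With B > 0 the curve also has no upper bound, although TOFR is recorded from 0 to 1. With the stated shape it cannot reproduce the dose pattern in the protocol's own background.

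A time to 0.9 can still be solved for the five active doses, but it comes from a level shift on one shared curve and is probably biased. The amount and direction of the bias are not established, because they depend on recovery curves not yet seen. The time comparisons assume equal starting TOFR across doses and use the quoted means for shape only. The algebra on placebo, slope and the time-0 gap needs neither assumption, but it does take A and B as common to all doses, as printed.

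**What to change.** Replace the model in Section 7 before the data are analysed. Either of two routes would do; the curve family is the trial statistician's choice.

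1. **Model the TOFR curve.** Let dose act on the recovery rate or time scale. Anchor the curve at the measured TOFR before study drug, include placebo as its own category or through a dose function defined at 0, and adjust for TOFC stratum. A rate of the form k0 + k1·dose^h is one example. In the illustration it fitted all six groups together and, from a start of 0.4, returned 8.57, 5.75, 3.80, 2.47 and 1.60 min against true 8.57, 5.68, 3.76, 2.49 and 1.65. The data came from the same family, so this shows only that such a fit is feasible.
2. **Analyse time to 0.9 directly** in all six groups, with censoring at 10 minutes and adjustment for TOFC and baseline TOFR.

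State which analysis serves the primary comparison with placebo, and what stratified means if the word stays. As a minor addition, list the serial TOFR readings in Section 20. Section 6 describes electromyography "which measures the TOF ratio every 20 seconds" and says TOFR is recorded after study drug, but the Section 20 list has no TOFR value between study drug and PACU. The REDCap form may already hold them.

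The cost is SAP wording and a somewhat more complex fit. No extra patients or procedures are needed.
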